4.4. Invasive mechanical ventilation

Concept ID	Concept name
4230167	Artificial respiration
40481547	Dependence on ventilator
4080957	Endotracheal respiratory assistance
4168966	Endotracheal tube present
4232550	Home visit for mechanical ventilation care
4235361	Hyperventilation therapy for traumatic brain injury
37116689	Insertion of endotracheal ventilation catheter
40487536	Intubation of respiratory tract
4332501	Management of noninvasive mechanical ventilation
37206832	Mechanical insufflation exsufflation
765576	Orotracheal intubation using bougie device
4219858	Problem with patient ventilator
2788037	Respiratory Ventilation, 24-96 Consecutive Hours
2788038	Respiratory Ventilation, Greater than 96 Consecutive Hours
2788036	Respiratory Ventilation, Less than 24 Consecutive Hours
4237618	Ventilator care
4251737	Ventilator care management
44791135	Ventilatory support
4072633	Weaning from mechanically assisted ventilation

4.5. ECMO

Concept ID	Concept name
4338595	Cardiac support using extracorporeal membrane oxygenation circuitry
4052536	Extracorporeal membrane oxygenation

44811012	Fluoroscopy guided percutaneous insertion of cannula for extracorporeal membrane oxygenation
----------	--

4.6. Venous thromboembolic (pulmonary embolism and deep vein thrombosis)

Concept ID	Concept name
40481089	Embolism from thrombosis of vein of lower extremity
440417	Pulmonary embolism
254662	Pulmonary infarction
318775	Venous embolism
444247	Venous thrombosis
36713113	Saddle embolus of pulmonary artery
35615055	Saddle embolus of pulmonary artery with acute cor pulmonale

4.7. Death

Concept ID	Concept name
4306655	Death

5. Comorbidities

5.1. Hypertension

Concept ID	Concept name
316866	Hypertensive disorder
4322024	Pulmonary hypertension
42709887	Hypertensive complication

5.2. Type 2 diabetes mellitus

Concept ID	Concept name
43021173	History of diabetes mellitus type 2
42539022	History of diabetes related lower limb amputation
46270562	History of small vessel disease due to diabetes mellitus
201820	Diabetes mellitus
442793	Complication due to diabetes mellitus
443238	Diabetic - poor control

5.3. Chronic obstructive pulmonary disease (COPD)

Concept ID	Concept name
255573	Chronic obstructive lung disease
258780	Emphysematous bronchitis

5.4. Asthma

Concept ID	Concept name
317009	Asthma
4235703	Asthma management
4279553	Eosinophilic asthma

5.5. Chronic kidney disease

Concept ID	Concept name
194385	Aneurysm of renal artery
46271022	Chronic kidney disease
192279	Disorder of kidney due to diabetes mellitus
4263367	Glomerulonephritis
261071	Glomerulosclerosis
201313	Hypertensive renal disease
4103224	Interstitial nephritis
193253	Nephritis
195314	Nephrotic syndrome
192359	Renal failure syndrome
45768812	Anemia in chronic kidney disease

5.6. Heart disease

Concept ID	Concept name
321588	Heart disease
443563	Arteriosclerosis of coronary artery bypass graft

5.7. Obesity

Concept ID	Concept name
4099154	Body weight
4060985	Body mass index 30+ - obesity
4256640	Body mass index 40+ - severely obese
45766204	Lymphedema associated with obesity
433736	Obesity
4176962	Obesity associated disorder
4081038	Pulmonary hypertension with extreme obesity

5.8. Smoker

Concept ID	Concept name
4298794	Smoker
4222303	Non-smoker

5.9. Autoimmune conditions

Concept ID	Concept name
374919	Multiple sclerosis
4137275	Vasculitis
443394	Addison's disease
194992	Celiac disease
201606	Crohn's disease
46269889	Complication due to Crohn's disease
46269999	History of Crohns disease
4232076	Graves' disease
135215	Hashimoto thyroiditis
76685	Myasthenia gravis
432893	Myasthenic syndrome due to another disorder
432295	Pernicious anemia
75614	Acrodermatitis continua
140168	Psoriasis
81931	Psoriasis with arthropathy
4297650	Cutaneous atrophy due to rheumatoid arthritis
4334806	Deformity of foot due to rheumatoid arthritis
46273442	Deformity of hand due to rheumatoid arthritis
4058299	H/O: rheumatoid arthritis
4107913	Myopathy due to rheumatoid arthritis
4102493	Polyneuropathy in rheumatoid arthritis
80809	Rheumatoid arthritis
4083556	Seronegative rheumatoid arthritis
4035611	Seropositive rheumatoid arthritis
438688	Sarcoidosis
4262578	Sarcoid arthropathy
45772123	Sarcoid iridocyclitis
4105005	Multiple cranial nerve palsies in sarcoidosis
46272236	Ischemic nephropathy
4331739	Linear scleroderma
441928	Localized scleroderma
255304	Lung disease with systemic sclerosis
4105026	Myopathy due to systemic sclerosis
46270482	Polyneuropathy due to systemic sclerosis
134442	Systemic sclerosis

4063582	Systemic sclerosis induced by drugs and chemicals
254443	Sjögren's syndrome
46273369	Endocarditis due to systemic lupus erythematosus
4145240	Renal tubulo-interstitial disorder in systemic lupus erythematosus
257628	Systemic lupus erythematosus
201254	Type 1 diabetes mellitus
435216	Disorder due to type 1 diabetes mellitus
40484648	Type 1 diabetes mellitus uncontrolled
46273477	Complication due to ulcerative colitis
81893	Ulcerative colitis
46273478	Rectal hemorrhage due to ulcerative colitis
46274082	Intestinal obstruction due to ulcerative colitis
46269952	Fistula of intestine due to ulcerative colitis
4116142	Arthropathy in ulcerative colitis

6. Respiratory support

6.1. Noninvasive respiratory support

Concept ID	Concept name
4239130	Oxygen therapy

6.2. Invasive respiratory support

Concept ID	Concept name
4338595	Cardiac support using extracorporeal membrane oxygenation circuitry
4052536	Extracorporeal membrane oxygenation
44811012	Fluoroscopy guided percutaneous insertion of cannula for extracorporeal membrane oxygenation
4230167	Artificial respiration
40481547	Dependence on ventilator
4080957	Endotracheal respiratory assistance
4168966	Endotracheal tube present
4232550	Home visit for mechanical ventilation care
4235361	Hyperventilation therapy for traumatic brain injury
37116689	Insertion of endotracheal ventilation catheter
40487536	Intubation of respiratory tract
4332501	Management of noninvasive mechanical ventilation
37206832	Mechanical insufflation exsufflation
765576	Orotracheal intubation using bougie device
4219858	Problem with patient ventilator
4237618	Ventilator care
4251737	Ventilator care management
44791135	Ventilatory support

4072633	Weaning from mechanically assisted ventilation
4166281	Anterior tracheostomy
4115488	Emergency tracheostomy
4337047	Insertion of tracheostomy tube
4168864	Lateral tracheostomy
4199580	Mediastinal tracheostomy
4065590	Permanent tracheostomy
2743216	Removal of Tracheostomy Device from Trachea, Via Natural or Artificial Opening
4311023	Revision of stoma of trachea
4195473	Temporary tracheostomy
4208093	Tracheostomy, emergency procedure by transtracheal approach

Appendix 2 ENCePP Checklist for Study Protocols

ENCEPP Checklist for Study Protocols (Revision 4)

Adopted by the ENCePP Steering Group on 15/10/2018

The [European Network of Centres for Pharmacoepidemiology and Pharmacovigilance \(ENCEPP\)](#) welcomes innovative designs and new methods of research. This Checklist has been developed by ENCePP to stimulate consideration of important principles when designing and writing a pharmacoepidemiological or pharmacovigilance study protocol. The Checklist is intended to promote the quality of such studies, not their uniformity. The user is also referred to the [ENCEPP Guide on Methodological Standards in Pharmacoepidemiology](#), which reviews and gives direct electronic access to guidance for research in pharmacoepidemiology and pharmacovigilance.

For each question of the Checklist, the investigator should indicate whether or not it has been addressed in the study protocol. If the answer is “Yes”, the section number of the protocol where this issue has been discussed should be specified. It is possible that some questions do not apply to a particular study (for example, in the case of an innovative study design). In this case, the answer ‘N/A’ (Not Applicable) can be checked and the “Comments” field included for each section should be used to explain why. The “Comments” field can also be used to elaborate on a “No” answer.

This Checklist should be included as an Annex by marketing authorisation holders when submitting the protocol of a non-interventional post-authorisation safety study (PASS) to a regulatory authority (see the [Guidance on the format and content of the protocol of non-interventional post-authorisation safety studies](#)). The Checklist is a supporting document and does not replace the format of the protocol for PASS presented in the Guidance and Module VIII of the Good pharmacovigilance practices (GVP).

Study title: Systemic glucocorticoids use in the treatment of COVID-19 and risks of adverse outcomes in COVID-19 patients in the primary and secondary care setting

EU PAS Register® number: Not yet registered

Study reference number (if applicable):

Section 1: Milestones	Yes	No	N/A	Section Number
1.1 Does the protocol specify timelines for				4.0
1.1.1 Start of data collection ⁴				
1.1.2 End of data collection ⁵				
1.1.3 Progress report(s)				
1.1.4 Interim report(s)				
1.1.5 Registration in the EU PAS Register®				
1.1.6 Final report of study results.				

Comments:

--

Section 2: Research question	Yes	No	N/A	Section Number
2.1 Does the formulation of the research question and objectives clearly explain:				5.0 and 6.0
2.1.1 Why the study is conducted? (e.g. to address an important public health concern, a risk identified in the risk management plan, an emerging safety issue)				
2.1.2 The objective(s) of the study?				
2.1.3 The target population? (i.e. population or subgroup to whom the study results are intended to be generalised)				
2.1.4 Which hypothesis(-es) is (are) to be tested?				

⁴ Date from which information on the first study is first recorded in the study dataset or, in the case of secondary use of data, the date from which data extraction starts.

⁵ Date from which the analytical dataset is completely available.

Section 2: Research question	Yes	No	N/A	Section Number
2.1.5 If applicable, that there is no a priori hypothesis?				

Comments:

Section 3: Study design	Yes	No	N/A	Section Number
3.1 Is the study design described? (e.g. cohort, case-control, cross-sectional, other design)				7.0
3.2 Does the protocol specify whether the study is based on primary, secondary or combined data collection?				7.0
3.3 Does the protocol specify measures of occurrence? (e.g., rate, risk, prevalence)				7.7.2.2
3.4 Does the protocol specify measure(s) of association? (e.g. risk, odds ratio, excess risk, rate ratio, hazard ratio, risk/rate difference, number needed to harm (NNH))				7.7.2.2
3.5 Does the protocol describe the approach for the collection and reporting of adverse events/adverse reactions? (e.g. adverse events that will not be collected in case of primary data collection)				

Comments:

Section 4: Source and study populations	Yes	No	N/A	Section Number
4.1 Is the source population described?				7.1/7.4
4.2 Is the planned study population defined in terms of:				7.2
4.2.1 Study time period				
4.2.2 Age and sex				
4.2.3 Country of origin				
4.2.4 Disease/indication				
4.2.5 Duration of follow-up				

Section 4: Source and study populations	Yes	No	N/A	Section Number
4.3 Does the protocol define how the study population will be sampled from the source population? (e.g. event or inclusion/exclusion criteria)				7.2.2

Comments:

4.1 Including the Data Sources section where details on conversion are given				
Section 5: Exposure definition and measurement	Yes	No	N/A	Section Number
5.1 Does the protocol describe how the study exposure is defined and measured? (e.g. operational details for defining and categorising exposure, measurement of dose and duration of drug exposure)				7.3.2
5.2 Does the protocol address the validity of the exposure measurement? (e.g. precision, accuracy, use of validation sub-study)				
5.3 Is exposure categorised according to time windows?				
5.4 Is intensity of exposure addressed? (e.g. dose, duration)				7.3.2
5.5 Is exposure categorised based on biological mechanism of action and taking into account the pharmacokinetics and pharmacodynamics of the drug?				
5.6 Is (are) (an) appropriate comparator(s) identified?				7.3.2

Comments:

--

Section 6: Outcome definition and measurement	Yes	No	N/A	Section Number
6.1 Does the protocol specify the primary and secondary (if applicable) outcome(s) to be investigated?				7.3.3/7.3.4
6.2 Does the protocol describe how the outcomes are defined and measured?				7.3.3/7.3.4

Section 6: Outcome definition and measurement		Yes	No	N/A	Section Number
6.3	Does the protocol address the validity of outcome measurement? (e.g. precision, accuracy, sensitivity, specificity, positive predictive value, use of validation sub-study)				
6.4	Does the protocol describe specific outcomes relevant for Health Technology Assessment? (e.g. HRQoL, QALYs, DALYS, health care services utilisation, burden of disease or treatment, compliance, disease management)				

Comments:

--

Section 7: Bias		Yes	No	N/A	Section Number
7.1	Does the protocol address ways to measure confounding? (e.g. confounding by indication)				7.9
7.2	Does the protocol address selection bias? (e.g. healthy user/adherer bias)				7.9
7.3	Does the protocol address information bias? (e.g. misclassification of exposure and outcomes, time-related bias)				7.9

Comments:

--

Section 8: Effect measure modification		Yes	No	N/A	Section Number
8.1	Does the protocol address effect modifiers? (e.g. collection of data on known effect modifiers, subgroup analyses, anticipated direction of effect)				

Comments:

--

Section 9: Data sources		Yes	No	N/A	Section Number
9.1	Does the protocol describe the data source(s) used in the study for the ascertainment of:				
9.1.1	Exposure? (e.g. pharmacy dispensing, general practice prescribing, claims data, self-report, face-to-face interview)				7.4
9.1.2	Outcomes? (e.g. clinical records, laboratory markers or values, claims data, self-report, patient interview including scales and questionnaires, vital statistics)				7.4
9.1.3	Covariates and other characteristics?				7.4
9.2	Does the protocol describe the information available from the data source(s) on:				
9.2.1	Exposure? (e.g. date of dispensing, drug quantity, dose, number of days of supply prescription, daily dosage, prescriber)				7.4
9.2.2	Outcomes? (e.g. date of occurrence, multiple event, severity measures related to event)				
9.2.3	Covariates and other characteristics? (e.g. age, sex, clinical and drug use history, co-morbidity, co-medications, lifestyle)				7.3.5/7.4
9.3	Is a coding system described for:				
9.3.1	Exposure? (e.g. WHO Drug Dictionary, Anatomical Therapeutic Chemical (ATC) Classification System)				7.3.2
9.3.2	Outcomes? (e.g. International Classification of Diseases (ICD), Medical Dictionary for Regulatory Activities (MedDRA))				
9.3.3	Covariates and other characteristics?				
9.4	Is a linkage method between data sources described? (e.g. based on a unique identifier or other)				

Comments:

--

Section 10: Analysis plan	Yes	No	N/A	Section Number
10.1 Are the statistical methods and the reason for their choice described?				7.7
10.2 Is study size and/or statistical precision estimated?				7.5
10.3 Are descriptive analyses included?				7.7
10.4 Are stratified analyses included?				7.7
10.5 Does the plan describe methods for analytic control of confounding?				7.7.2.2
10.6 Does the plan describe methods for analytic control of outcome misclassification?				
10.7 Does the plan describe methods for handling missing data?				
10.8 Are relevant sensitivity analyses described?				

Comments:

--

Section 11: Data management and quality control	Yes	No	N/A	Section Number
11.1 Does the protocol provide information on data storage? (e.g. software and IT environment, database maintenance and anti-fraud protection, archiving)				7.6/8.0
11.2 Are methods of quality assurance described?				7.8
11.3 Is there a system in place for independent review of study results?				

Comments:

--

Section 12: Limitations	Yes	No	N/A	Section Number
12.1 Does the protocol discuss the impact on the study results of:				7.9
12.1.1 Selection bias?				
12.1.2 Information bias?				

Section 12: Limitations	Yes	No	N/A	Section Number
12.1.3 Residual/unmeasured confounding? (e.g. anticipated direction and magnitude of such biases, validation sub-study, use of validation and external data, analytical methods).				
12.2 Does the protocol discuss study feasibility? (e.g. study size, anticipated exposure uptake, duration of follow-up in a cohort study, patient recruitment, precision of the estimates)				

Comments:

--

Section 13: Ethical/data protection issues	Yes	No	N/A	Section Number
13.1 Have requirements of Ethics Committee/ Institutional Review Board been described?				
13.2 Has any outcome of an ethical review procedure been addressed?				
13.3 Have data protection requirements been described?				8.0

Comments:

--

Section 14: Amendments and deviations	Yes	No	N/A	Section Number
14.1 Does the protocol include a section to document amendments and deviations?				3.0

Comments:

--

Section 15: Plans for communication of study results	Yes	No	N/A	Section Number
15.1 Are plans described for communicating study results (e.g. to regulatory authorities)?				10.0

Section 15: Plans for communication of study results	Yes	No	N/A	Section Number
15.2 Are plans described for disseminating study results externally, including publication?				10.0

Appendix 3 Alternative treatments for COVID-19

Treatment	
Antiviral therapy (AV)	
P01BA02	Hydroxychloroquine
	Hydroxychloroquine + azithromycin combination
	Hydroxychloroquine + fluoroquinolones combination
	Hydroxychloroquine + amoxicillin combination
	Hydroxychloroquine + ceftriaxone combination
P01BA01	Chloroquine
P02CF01	Ivermectin
J02AC02	Itraconazole
J05AX27	Favipiravir
Not yet assigned	Remdesivir
J05AP01	Ribavirin
J05AH02	Oseltamivir
J05AR10	Lopinavir + ritonavir combination
J05AF09	Emtricitabine
G03XC01	Raloxifene
Antibiotic therapy (AB)	
J01CA04	Amoxicillin
J01MA01	Ofloxacin
J01MA02	Ciprofloxacin
J01MA03	Pefloxacin
J01MA04	Enoxacin
J01MA05	Temafloxacin

J01MA06	Norfloxacin
J01MA07	Lomefloxacin
J01MA08	Fleroxacin
J01MA09	Sparfloxacin
J01MA10	Rufloxacin
J01MA11	Grepafloxacin
J01MA12	Levofloxacin
J01MA13	Trovafloxacin
J01MA14	Moxifloxacin
J01MA15	Gemifloxacin
J01MA16	Gatifloxacin
J01MA17	Prulifloxacin
J01MA18	Pazufloxacin
J01MA19	Garenoxacin
J01MA21	Sitafoxacin
J01MA22	Tosufloxacin
J01MA23	Delafloxacin
J01DD04	Ceftriaxone
J01FA10	Azithromycin
Immune-based therapy (IB)	
L04AC07	Tocilizumab
L04AC14	Sarilumab
L04AC11	Siltuximab
L04AA37	Baricitinib
L04AA29	Tofacitinib
L04AB04	Adalimumab

L04AB01	Etanercept
L04AB02	Infliximab
L04AC05	Ustekinumab
L04AC03	Anakinra
L01XE27	Ibrutinib
L01XE18	Ruxolitinib
L01XC07	Bevacizumab
L04AA27	Fingolimod
L04AA25	Eculizumab
L04AX02	Thalidomide
L04AD02	Tacrolimus
L03AB02	Interferon Beta Natural
L03AB07	Interferon Beta-1a
L03AB08	Interferon Beta-1b
L03AB13	Peginterferon Beta-1a
L03AB15	Ropeginterferon Alfa-2b
L03AB12	Albinterferon Alfa-2b
L03AB14	Cepeginterferon Alfa-2b
L03AB01	Interferon Alfa Natural
L03AB04	Interferon Alfa-2a
L03AB05	Interferon Alfa-2b
L03AB06	Interferon Alfa-N1
L03AB09	Interferon Alfacon-1
L03AB11	Peginterferon Alfa-2a
L03AB10	Peginterferon Alfa-2b
L03AA09	Sargramostim

A11CC05	Colecalciferol
A02BA01	Cimetidine
A02BA02	Ranitidine
A02BA03	Famotidine
A02BA04	Nizatidine
A02BA06	Roxatidine
Antithrombotic therapy (AT)	
B01AA01	Dicoumarol
B01AA07	Acenocoumarol
B01AA03	Warfarin
B01AB01	Heparin
B01AB05	Enoxaparin
B01AB04	Dalteparin
B01AB12	Bemiparin
B01AB06	Nadroparin
B01AB07	Parnaparin
B01AB08	Reviparin
B01AB09	Danaparoid
B01AB10	Tinzaparin
B01AB11	Sulodexide
B01AB51	Heparin Combinations
B01AC01	Ditazole
B01AC02	Cloricromen
B01AC03	Picotamide
B01AC04	Clopidogrel

B01AC05	Ticlopidine
B01AC06	Acetylsalicylic Acid
B01AC07	Dipyridamole
B01AC08	Carbasalate Calcium
B01AC09	Epoprostenol
B01AC10	Indobufen
B01AC11	Iloprost
B01AC13	Abciximab
B01AC15	Aloxiprin
B01AC16	Eptifibatide
B01AC17	Tirofiban
B01AC18	Triflusal
B01AC19	Beraprost
B01AC21	Treprostinil
B01AC22	Prasugrel
B01AC23	Cilostazol
B01AC24	Ticagrelor
B01AC25	Cangrelor
B01AC26	Vorapaxar
B01AC27	Selexipag
B01AD01	Streptokinase
B01AD02	Alteplase
B01AD03	Anistreplase
B01AD04	Urokinase
B01AD05	Fibrinolysin

B01AD06	Brinase
B01AD07	Reteplase
B01AD08	Saruplase
B01AD09	Ancrod
B01AD10	Drotrecogin Alfa (Activated)
B01AD11	Tenecteplase
B01AD12	Protein C
B01AD02	Alteplase
B01AD11	Tenecteplase
B01AD07	Reteplase
B01AE01	Desirudin
B01AE02	Lepirudin
B01AE03	Argatroban
B01AE04	Melagatran
B01AE05	Ximelagatran
B01AE06	Bivalirudin
B01AE07	Dabigatran Etxilate
B01AF01	Rivaroxaban
B01AF02	Apixaban
B01AF03	Edoxaban
B01AF04	Betrixaban
B01AX01	Defibrotide
B01AX04	Dermatan Sulfate
B01AX05	Fondaparinux
B01AX07	Caplacizumab

B02AA01	Aminocaproic Acid
B02AA02	Tranexamic Acid
B02AB04	Camostat
J06BA01	Immunoglobulins, Normal Human, For Extravascular Adm.
J06BA02	Immunoglobulins, Normal Human, For Intravascular Adm.
L03AX03	BCG Vaccine
Antihypertensives (AH)	
C03AA01	Bendroflumethiazide
C03AA02	Hydroflumethiazide
C03AA03	Hydrochlorothiazide
C03AA04	Chlorothiazide
C03AA05	Polythiazide
C03AA06	Trichlormethiazide
C03AA07	Cyclopenthiiazide
C03AA08	Methyclothiazide
C03AA09	Cyclothiazide
C03AA13	Mebutizide
C08CX01	Mibefradil
C08DA01	Verapamil
C08DA02	Gallopamil
C08DA51	Verapamil, Combinations
C08DB01	Diltiazem
C08EA01	Fendiline
C08EA02	Bepridil
C09AA01	Captopril

C09AA02	Enalapril
C09AA03	Lisinopril
C09AA04	Perindopril
C09AA05	Ramipril
C09AA06	Quinapril
C09AA07	Benazepril
C09AA08	Cilazapril
C09AA09	Fosinopril
C09AA10	Trandolapril
C09AA11	Spirapril
C09AA12	Delapril
C09AA13	Moexipril
C09AA14	Temocapril
C09AA15	Zofenopril
C09AA16	Imidapril
C09CA01	Losartan
C09CA02	Eprosartan
C09CA03	Valsartan
C09CA04	Irbesartan
C09CA05	Tasosartan
C09CA06	Candesartan
C09CA07	Telmisartan
C09CA08	Olmesartan Medoxomil
C09CA09	Azilsartan Medoxomil
C09CA10	Fimasartan

Statins (S)	
C10AA01	Simvastatin
C10AA02	Lovastatin
C10AA03	Pravastatin
C10AA04	Fluvastatin
C10AA05	Atorvastatin
C10AA06	Cerivastatin
C10AA07	Rosuvastatin
C10AA08	Pitavastatin
Antidiabetic (AD)	
A10BA02	Metformin
A10BH01	Sitagliptin
A10BH02	Vildagliptin
A10BH03	Saxagliptin
A10BH04	Alogliptin
A10BH05	Linagliptin
A10BK01	Dapagliflozin
A10BK02	Canagliflozin
A10BK03	Empagliflozin
A10BK04	Ertugliflozin
A10BJ01	Exenatide
A10BJ02	Liraglutide
A10BJ03	Lixisenatide
A10BJ04	Albiglutide
A10BJ05	Dulaglutide

A10BJ06

Semaglutide

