7.7.8 Sensitivity analysis

For objective 2 and 3, with regards to the reference group for incidence rates

As a sensitivity analysis, the reference group for incidence rates will be replaced with ‘other immunotherapies’ (see Appendix 3 for details).

For prevalent users’ cohorts, the definition of remote users:

A sensitivity analysis to exclude those patients for whom short term duration of corticosteroid use (14 days) is identified prior to COVID-19 diagnosis.

For objectives 2 and 3, if the number of patients censored due to switching is higher than 70%, a sensitivity analysis will be performed, namely an intention to treat approach (ITT), such that after initial exposure is defined to allocate patients to one of the four treatment groups, the denominator is then person-time observed (irrespective of treatment status), rather than person-time treated.

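### Appendix 3 files antifibrinolytics, immunoglobulins and BCG as antithrombotics, and vitamin D and H2 blockers as immune-based drugs, which leaves the immunotherapy reference group of 7.7.8 badly specified

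*Protocol*

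**What the plan says.** Protocol Appendix 3 groups the other COVID-19 treatments into seven classes.

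- **Antithrombotic therapy (AT).** After the B01 codes, and before the next heading ("Antihypertensives (AH"), come "Aminocaproic Acid" (B02AA01), "Tranexamic Acid" (B02AA02), camostat (printed as B02AB04), two normal human immunoglobulins (J06BA01 and J06BA02, the second being "Immunoglobulins, Normal Human, For Intravascular Adm") and BCG vaccine (L03AX03). No heading separates them from the B01 drugs.
- **Immune-based therapy (IB).** After a run of L-coded agents come "Colecalciferol" (A11CC05) and five H2 blockers (A02BA01 to A02BA04, and A02BA06).

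The classes are used in three places. Section 7.3.2.2 builds additional treatment cohorts from them. The primary objective (6.2) describes the number and type of concomitant medications. Section 7.7.8 says that "the reference group for incidence rates will be replaced with" a group called 'other immunotherapies' and points to Appendix 3 for its content. No class in the appendix has that name.

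**The concern.** Some entries contradict the heading they stand under. Antifibrinolytics act against the breakdown of clots, so counting their users as antithrombotic users reverses the meaning of the class. Immunoglobulins and BCG are immune products, and BCG is the only L03 code in the appendix outside IB. In the other direction, vitamin D and H2 blockers stand among biologics, kinase inhibitors and interferons.

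Two outputs are at stake. First, any table of concomitant antithrombotic use would carry mislabelled patients. Second, if 'other immunotherapies' means IB, the sensitivity reference group takes in people whose only qualifying drug is vitamin D or an acid suppressant, and leaves out people on immunoglobulins or BCG. Section 7.3.3 lists gastritis, gastric ulcer and GI bleed as outcomes. H2 blockers are prescribed for gastric conditions, so their users bring a gastric risk tied to that indication. Rates of those outcomes in the reference group would then not describe patients on immunotherapy.

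**Working it through.** The protocol states no figure on this point, so there is none to reproduce. The check is a count of Appendix 3 by ATC prefix, followed by a range for the share of patients.

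**Count of entries**

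- IB: 38 entries, made up of 15 L03, 14 L04, 3 L01, 5 A02 and 1 A11.
  - L-coded: 15 + 14 + 3 = 32, and 32/38 = 84.2%.
  - Vitamin D and H2 blockers: 1 + 5 = 6, and 6/38 = 15.8%.
  - Counting only L03 and L04 as immunotherapy: 29/38 = 76.3%.
- AT: 74 rows, made up of 68 B01, 3 B02, 2 J06 and 1 L03. Three B01 codes are printed twice (B01AD02, B01AD07, B01AD11), which leaves 71 distinct codes. Six rows are not B01.

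**Share of patients in the 7.7.8 group**

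Let r be the number of patients who qualify only through vitamin D or an H2 blocker, divided by the number with at least one L-coded drug. The share of the group not on an L-coded drug is r/(1 + r). The protocol gives no user counts by drug, so r is an assumption:

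| r (assumed) | r/(1 + r) |
|---|---|
| 0.1 | 0.1/1.1 = 9% |
| 0.5 | 0.5/1.5 = 33% |
| 1 | 1/2 = 50% |
| 2 | 2/3 = 67% |
| 10 | 10/11 = 91% |

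The break-even is r = 1.

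**What the protocol says that bears on r**

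- Section 7.5 gives about 2,000 hospital patients out of 153,759, that is 2,000/153,759 = 1.3%. The other seven databases are ambulatory.
- Section 7.4 takes drug data in Belgium and France from GP prescriptions, and says for IPCI and SIDIAP that drugs not prescribed in the GP setting may be underreported. Biologics, kinase inhibitors and interferons are the kind of drug such data would tend to miss. Vitamin D and H2 blockers are ordinary GP items.
- Section 7.3.2.3 counts a patient as exposed after one prescription. It says so for the four main groups; carrying the rule over to 7.7.8 is an inference.

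These facts point towards a larger r but do not fix its value.

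**Effect on the main analysis**

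The four exposure groups of 7.3.2.3 pool all drug classes into 'other treatments'. Moving an entry from one class to another leaves them unchanged. Removing the antifibrinolytics altogether changes the group only of a patient whose sole other treatment is an antifibrinolytic.

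**Count after correction**

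- IB: 38 - 6 + 3 = 35 entries.
- AT: 74 - 2 - 3 = 69 rows, with camostat still to be settled.

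**The case against.** The strongest reply is that the classes are not meant to follow ATC groups. Section 7.3.2.2 says they were taken from another project's review of proposed COVID-19 treatments, and the antiviral class also holds raloxifene and ivermectin. Vitamin D and H2 blockers may stand under IB because of a proposed immune role. This stands in part: for those six entries a filing error is not proven. It does not make them suitable for a reference group labelled immunotherapy, and it cannot explain antifibrinolytics under an antithrombotic heading.

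Second, the link from 7.7.8 to IB is inferred, and the SAP may list the codes. That is fair. But 7.7.8 sends the reader to Appendix 3 for the details, and the appendix offers no better match.

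Third, long-term vitamin D or acid suppression might not count as COVID-19 treatment, since 7.3.2.3 allows drugs for other indications in the untreated group. However, 7.3.2.2 assigns exposure by presence on the list, and 7.3.2.1 says that indication is not captured, so the plan gives no way to separate the two uses.

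Fourth, the study is expressly non-comparative (6.3, 7.9.1), which limits the harm. That stands. The rates of a named reference group will still be read as rates for that treatment.

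A reader might go further and infer that the 7.7.8 group is mostly not immunotherapy. The documents do not support that. By entries it is false, since 84.2% of IB is L-coded. By patients it needs r above 1. For instance, assuming 5% to 15% on vitamin D or an H2 blocker against 1% on a true immune drug gives 5/6 = 83% to 15/16 = 94%, but neither input is in the protocol and only one of them is varied. Nor do the AT entries dilute the immune group; their effect there is to leave immunoglobulins and BCG out of it.

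Finally, a subheading before the last AT rows that is missing from the text available cannot be fully excluded. Nothing indicates one, and the IB point would stand regardless.

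**Conclusion.** The code list is wrong for two antifibrinolytics, two immunoglobulins and BCG under AT. Six further entries under IB do not belong in a reference group called 'other immunotherapies'. Followed as written, the plan would report antifibrinolytic users as antithrombotic users. If IB is the intended source, it would also build the 7.7.8 group with vitamin D and H2-blocker users in it, and without immunoglobulin and BCG users.

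The size of the second effect is not known. It runs from 9% to 91% of the group over assumed r from 0.1 to 10, and the ambulatory, GP-based data make a large share plausible. The conclusion rests on reading 'other immunotherapies' as IB and on applying list membership as the exposure rule. The primary objective is touched only through class-level description of concomitant drugs. The main incidence rates of objectives 2 and 3 are essentially unaffected.

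**What to change.** In Appendix 3:

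- Take B02AA01 and B02AA02 out of AT.
- File J06BA01, J06BA02 and L03AX03 under IB.
- Check the placement of camostat against the source classification that 7.3.2.2 cites.
- List A11CC05 and the five A02BA codes as a separate class. They can stay in the pooled 'other treatments' group.

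In 7.7.8, name the exact codes that make up 'other immunotherapies', and exclude A11CC05 and the A02BA codes from them.

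The cost is a code-list edit before the final extraction. The one downside is that the sensitivity reference group may become smaller. If it is then too small to report in the ambulatory databases, that is itself worth stating.
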